Methamphetamine (MA) addiction is a chronic relapsing conditions that causes devastating physical and psychiatric harm to affected individuals [1]. These include increased risk of psychosis [2], depression/anxiety [1], suicidal behavior [3], completed suicide [4], and even all-cause mortality when compared to users of cocaine, alcohol or cannabis [5]. However, since discontinuation of MA use leads to negative emotional states, abstinence from MA poses intense difficulty for dependent individuals. Given these observations, basic and clinical research studies have focused on the development of new pharmacological interventions [6], but have not led to Food and Drug Administration (FDA) approved pharmacotherapies that improve cognitive deficits and depressive symptoms during MA discontinuation [7].

Methamphetamine has deleterious effects on dopaminergic brain systems [8], and prolonged amphetamine exposure is associated with Parkinson's disease [9]. Animal studies suggest that MA use predisposes to Parkinson's via degeneration of the midbrain dopaminergic neurons that project to striatum [10]. A recent epidemiologic study found a significant correlation between the development of Parkinson's disease (165% higher risk) in MA users followed for up to 10 years [11]. This finding was replicated in a larger sample of MA users (n=40,472) versus an appendicitis group (n=207,831; hazard ratio=1.76), and even a cocaine group (n=35,335; hazard ratio=2.44) [12].

Converging evidence implicates mitochondrial dysfunction in MA toxicity [8, 13-15]. Mitochondrial pathways interact to cause MA-induced neuronal apoptosis and death [16]. MA inhibits enzyme complexes of the electron transport chain, resulting in dopaminergic neurotoxicity because electron transport chain inhibitors increase reactive species [17-19]. Inhibition of complex I activity by MA [16] also decreases ATP production. MA produces mitochondrial fragmentation in progenitor cells [20], releasing apoptogenic molecules from mitochondria [21].

Brain Phosphocreatine (PCr) Levels and Glutamate Excitotoxicity in Methamphetamine Use:

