adolescent [71] females. In one study, depressive symptoms were endorsed on the Addiction Severity Index (ASI) by 68% of female MA users [3]. In another, early-onset MA use in females was significantly associated with premorbid depressive disorders, while the same was *not* true for males [72]. Female MA users with depression are less likely to be employed, more likely to use MA to manage their mood, use more grams of MA per 30-day period, use MA more times per day on more consecutive days, and are more likely to be binge users [73]. The diagnosis and treatment of depression and anxiety in MA users is complicated by the fact that withdrawal-associated dysphoria is persistent, and may be the result of *MA-induced neurotoxicity* [74]. Therefore, an ideal intervention for depression and anxiety in the setting of MA addiction would be one that targeted *both* neurotoxicity and negative emotional states.

Research has shown that females may respond better to treatment of MA use disorders than males [60, 75]. In fact, patient gender predicts both treatment engagement and abstinence during rehabilitation [76], a gender difference *not* found in cocaine- or alcohol-dependent research samples [77]. As a result, the recommendation has been made to take gender into account in developing treatments for MA use disorders [60, 75].

Creatine is a Novel Strategy for Cognitive Enhancement and Neuronal Repair in MA Addiction:

Our preliminary data, combined with the extant literature, suggest that creatine administration is a safe, hypothesis-driven strategy for: (a) Increasing brain PCr, NAA and GABA levels, thus providing neuroprotection and neuronal repair; (b) Reducing both depression and anxiety symptoms; and (c) Improving cognitive deficits in female MA users. Based on evolving understanding of MA neurotoxicity, a novel therapeutic strategy that has been suggested is to utilize cognitive enhancement and neuronal repair as pharmacotherapy targets in stimulant addiction [56, 57]. This stems, in part, from the fact that solely addressing the drug's addictive properties may be insufficient to address the diverse neuropathological injuries caused by MA [15]. However, in the absence of approved medications for MA use disorders, an initial step toward pursuing this innovative strategy is to assess the clinical and translational impact of a neuroprotective agent such as creatine in MA users.

Summary Significance and Relevance for This Proposal:

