In addition to these **Specific Aims**, we will monitor subjects' MA use, as improvements in brain bioenergetics, mood/anxiety and may decrease MA usage. Therefore, we will record urine drug testing results, to determine whether creatine vs. placebo is associated with a greater number of MA-free tests during the 8 weeks of randomized treatment.

PARTICIPANT SELECTION CRITERIA

123 women will be randomly assigned in a 1:1 ratio to either creatine or placebo for eight weeks. Table 1 outlines eligibility criteria.

TABLE 1 INCLUSION AND EXCLUSION CRITERIA

INCLUSION CRITERIA:

- Female gender, ages 18-55 inclusive
- Current primary diagnosis of MA dependence or abuse, with MA preferred drug of abuse (Lifetime MA use > 20 grams)
- Current diagnosis of Major Depressive Disorder (MDD)
- Current HAMD score ≥ 10
- Clinical Global Impressions–Severity (CGI-S) depression score ≥ 4
- If taking a psychotropic medication for depressed mood, regimen must be stable for ≥ 4 weeks prior to randomization

EXCLUSION CRITERIA:

- Persons unable to provide adequate informed consent
- Persons who are at clinically significant suicidal or homicidal risk
- Primary substance-related diagnosis *other than* MA dependence or abuse
- Comorbid substance dependence diagnosis, other than nicotine (substance abuse diagnoses are not excluded)
- Positive pregnancy test, due to the unknown effects of MRI scanning on the unborn fetus
- Positive test for antibody to the Human Immunodeficiency Virus (HIV)
- History of renal disease
- Clinically significant medical or neurological illness identified by history, physical exam and laboratory testing
- Known or suspected intellectual disability, or developmental disorder, e.g. autism
- History of hypersensitivity reaction to creatine

WITHDRAWAL / EARLY TERMINATION CRITERIA:

- Withdrawal of informed consent
- Suicide attempt
- Psychiatric hospitalization
- Onset of bipolar disorder or psychotic disorder
- Positive pregnancy test
- Incarceration
- Inability to comply with study protocol

▪ Treatment with electroconvulsive therapy (ECT)▪ Increase in HAMD score > 25% from baseline▪ Serious adverse event

▪ HEALTHY CONTROL SUBJECTS:
 
▪ Female gender, ages 18-55 inclusive▪ No current or past DSM-5 diagnosis, as determined by clinical and structured interviews▪ No first-degree relatives with known or suspected DSM-5 diagnosis

DESIGN

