At the screening visit, an ECG will be conducted in order to examine the heart and ensure participant safety; an adult cardiologist will also evaluate all individuals during the screening phase. If during the MRI/MRS scans we unexpectedly discover something that warrants further inspection, we will refer the participant to her primary care provider for follow-up, along with the MRI/MRS report that shows the findings. Any costs related to following up on unexpected findings will be the responsibility of her and/or her insurance provider. In conjunction with the brain scans performed pre- and post-treatment, a brief battery of cognitive tests will be administered, to evaluate change associated with creatine or placebo. Trained psychometricians administer tests on the day of scanning. Scoring is done blind to subjects' group status, clinical ratings and imaging results. The cognitive testing battery instruments were

chosen because they are sensitive to frontal lobe integrity: the Wisconsin Card Sorting Task (WCST)[129], the Stroop Color-Word Test[130, 131], and the Wechsler Memory Scale (WMS-IV)[132]. Furthermore, the WCST[133], Stroop Test[134] and WMS-IV [90] each have been associated with performance deficits in MA users.

TABLE 2A Schedule of Procedures for Methamphetamine-dependent Females												
	Screening	Treatment Phase								Follow Up Phase		
Study Week →	-2 to 0^a	1*	2*	3*	4*	5*	6*	7*	8*	9	10	11
Informed Consent, Demographics	X											
Medical History & Physical Exam, ECG	X											
Hematology & Chemistries	X									X		
Phlebotomy for Creatinine Levels	X				X					X		
HIV	X											
Pregnancy Test and vital signs	X	X	X	X	X	X	X	X	X	X	X	X
PRISM Diagnostic Interview	X											
ASI	X									X		
Randomization to Creatine or Placebo	X											
Treatment with Creatine or Placebo		X	X	X	X	X	X	X	X			
Urine Drug Screen / Other Drug Use	X	X	X	X	X	X	X	X	X	X	X	X
Concomitant Medications	X	X	X	X	X	X	X	X	X	X	X	X
Food Frequency Questionnaire	X									X		
Cognitive Tests: WCST, STROOP and WMS-IV (with WASI vocabulary)***	X									X		
Adverse Events		X	X	X	X	X	X	X	X	X	X	X
Treatment Program Attendance	X	X	X	X	X	X	X	X	X	X	X	X
Clinical Scales: HAMD**, BAI**, CGI-S**, C-SSRS	X	X	X	X	X	X	X	X	X	X	X	X

³¹ P-MRS and ¹ H-MRS****	X									X		
*During the 8 Treatment Weeks, MA Subjects Have 2 Study Visits Per Week (separated by \geq 48 hours)												
**Procedure will be collected at one of the twice weekly visits												

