Overall Analytic Strategy: The analyses proposed are generalized estimating equations (GEE) regression modeling, which will be used for our longitudinal data analyses with group comparison across treatment visits for the variables of metabolite levels, depression/anxiety symptoms, and cognitive tests. GEE allows robust estimations of standard errors and permits adjustment for time-varying covariates. We assume that measurements made closer in time are more correlated than those made farther apart. Thus, first-order autoregressive structure is assumed. For our repeated measurement data, GEE fits a population-averaged model with working correlation structure to statistically evaluate the time effect of creatine supplementation. We will control for age, other drug abuse, anxiety scores, and tissue partial volume effects in each GEE model. Sidak multiple comparison procedure will be employed to adjust for family wise error (FWE) rate. The Sidak tests make conservative controls of FWE, giving slightly smaller adjusted p-values than the Bonferroni correction.

Overall Power and Sample Size Calculations: For this pilot study, considering a 20% attrition rate, 95 participants will be recruited to achieve a sample size of 75. To determine the minimum effect that would likely be detected with a sample size of 75, a power analysis was performed. Effect for the power analysis was specified as average baseline (over two measures) HAM-D scores compared with average HAM-D scores during active treatment (over eight measures). A gradual onset of effect during active treatment is assumed, starting with an effect of 0 and ending with an effect of 0.5, resulting in an average effect during treatment of 0.25. The effect to be tested was treated as a linear combination of the separate measures (y^*), and a pattern of correlation of 0.5 was used. This generated a standard deviation [105] for y^* that will be different from the within-occasion SD for Y itself. Then the effect magnitude specified was divided by the $SD(y^*)$ to generate an "effective" or de facto effect size, which resulted in an effect size of 1.09 with a power of 0.87.

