The facilities at the University of Utah that are available for the proposed research include the following: the Brain Institute, Assessment and Referral Services and UNI. The Brain Institute currently occupies 5,900 square feet of office and laboratory space in a building in the University of Utah Research Park adjacent to the Health Sciences campus. It also occupies clinical space in UNI, the site of the Brain Institute's PRISMA 3T MRI research scanner. Assessment and Referral Services [4] is a freestanding clinic within the Department of Psychiatry. It occupies 6000 square feet in downtown Salt Lake City close to public transportation and approximately three miles from the University of Utah. It consists of 20 full time staff and approximately 30 part time staff. Salt Lake Behavioral Health Services contracts with ARS to provide three different functions. One is to provide assessments and referrals for individuals in Salt Lake County who have been arrested for driving under the influence; or who are seeking substance abuse services voluntarily or due to other court mandates. The third is to provide Interim Group Services (IGS), which are free groups for individuals awaiting Salt Lake County funded substance abuse treatment services.

Recruitment of Participants:

Primarily, participants will be recruited from ARS. Staff at ARS will refer women who identify methamphetamine as their primary drug of choice to the study staff. In addition, women will be recruited from the Clinical Assessment Center (CAC) at UNI. Staff at CAC will contact members of the study team to inform them if a MA-using woman interested in participating. The study team member will then follow-up with the interested woman to arrange a screening assessment.

Study information flyers will also be hung at ARS, 12-step recovery program meeting locations, Fellowship Hall, other drug-use referral locations, and public transportation such as buses and trax. Additionally, participants will be recruited by radio advertisements on select radio stations in the Salt Lake City area.

Study details will also be available on utahbrain.org.

CONTROL OF INVESTIGATIONAL DRUG

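### The screening methamphetamine urine result is collected but neither stratified on nor adjusted for; the cost is lost precision, modest for mood and possibly larger for the MA-free-test count

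*Combined protocol and SAP*

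**What the plan says.** **Entry.** Table 1 asks for a "Current primary diagnosis of MA dependence or abuse, with MA preferred drug of abuse (Lifetime MA use > 20 grams"), with current major depression, HAMD of at least 10 and CGI-S of at least 4. No criterion concerns the date of last use, a urine result or a period of abstinence. Under Recruitment of Participants, staff at one assessment centre are to "inform them if a MA-using woman interested in participating", and flyers go up at "12-step recovery program meeting locations", among other places.

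**Background.** The opening paragraph reasons that "since discontinuation of MA use leads to negative emotional states", and the section on depression in female users says that "withdrawal-associated dysphoria is persistent".

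**Data and allocation.** The Table 2A row "Urine Drug Screen / Other Drug Use" is marked at screening and in every week to week 11. Study Procedures describes a randomisation list made before recruitment and names no stratification factor.

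**Analysis.** The Overall Analytic Strategy applies GEE to metabolites, mood and anxiety, and cognition, and says: "We will control for age, other drug abuse, anxiety scores, and tissue partial volume effects in each GEE model". The Aim 3 section spells out the terms: visit (baseline and week 8), creatine, and their interaction, which is the test of treatment. The only stratified analysis named is by depression. Urine results are recorded to "determine whether creatine vs. placebo is associated with a greater number of MA-free tests during the 8 weeks" of treatment. The Specific Aims call this exploratory, and no model or baseline term is given for it.

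**The concern.** If mood and drug use over eight weeks run differently in women who enter using MA and women who enter having stopped, MA status at entry is a prognostic factor. The plan measures it and leaves it unused. The listed term for other drug abuse is, on its natural reading, abuse of drugs other than MA. At stake are two things. One is precision. The other is how a particular result is read if the arms happen to differ in entry status. The exposure is greatest for the MA-free-test count, since the entry urine result is in effect a first reading of that outcome.

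**Working it through.** The plan states no figure for the MA-positive share or its prognostic strength, so there is nothing of its own to reproduce on this point. Its nearest figure, the HAM-D power calculation, is used below only as a scale.

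**Inputs from the documents:** 75 analysed (power section); 123 randomised 1:1 (Design); average treatment effect 0.25 and correlation 0.5 (power section); two visits a week for 8 weeks (Table 2A).

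**Assumed inputs:** share p of women MA-positive at entry, 0.3-0.7; gap g in HAMD change between positive and negative women, 0.3-0.8 of the within-group SD of change; alpha 0.05 two-sided.

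**1. Chance imbalance without stratification.** SD of the between-arm difference in positive share = sqrt(4p(1-p)/N), with a normal approximation.

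| N | SD (p = 0.3 or 0.7; p = 0.5) | over 10 points | over 20 points |
|---|---|---|---|
| 75 | 0.106; 0.115 | 35-39% | 6-8% |
| 123 | 0.083; 0.090 | 23-27% | 2-3% |

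**2. What an imbalance does to mood.** Shift in the unadjusted contrast = imbalance x g. At 20 points this is 0.2 x 0.3 = 0.06 to 0.2 x 0.8 = 0.16 SD of change. At 10 points it is 0.03-0.08 SD.

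For scale, put the planned effect in the same units. Take 0.25 as within-occasion SD units, exchangeable correlation 0.5, and the mean of eight treatment measures minus the mean of two baseline measures. Then the variance is 0.5625 + 0.75 - 2 x 0.5 = 0.3125, the SD is 0.559, and the standardised effect is 0.25/0.559 = 0.447. A 20-point imbalance is then worth 0.06/0.447 = 13% to 0.16/0.447 = 36% of the planned effect. (The plan states 1.09 with power 0.87. That does not reproduce from these inputs, but it is a separate matter and nothing here depends on it.)

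In 20,000 simulated trials with g = 0.5, those with an imbalance above 20 points had a mean error of 0.12 SD unadjusted and 0.00 adjusted.

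**3. Average precision for mood.** R² = p(1-p)g² / (1 + p(1-p)g²); equivalent sample = 75/(1 - R²).
- p = 0.3, g = 0.3: R² = 0.0189/1.0189 = 0.019, equivalent to 76 women.
- p = 0.5, g = 0.8: R² = 0.16/1.16 = 0.138, equivalent to 87 women.
- Power at an effect of 0.447 rises from 0.49 to 0.50-0.55.

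**4. MA-free-test count.** Assume MA-free shares from 0.6 v 0.5 up to 0.8 v 0.3 (entry-negative v entry-positive) and a within-group SD of 0.25-0.35. With gap D and SD s, R² = p(1-p)D² / (p(1-p)D² + s²).
- p = 0.3, D = 0.1, s = 0.35: 0.0021/0.1246 = 0.017, equivalent to 76 women.
- p = 0.5, D = 0.5, s = 0.25: 0.0625/0.125 = 0.50, equivalent to 150 women.
- A 20-point imbalance shifts the arm difference by 0.2 x D x 16 = 0.3 to 1.6 tests. The 16 assumes a test at both weekly visits, which Table 2A does not state.

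**5. Which adjustment works.** Where baseline is itself a response visit, as in Aim 3, the creatine x visit estimate with complete data is the between-arm difference in mean change. A subject-level covariate entered as a main effect adds the same amount at both visits and cancels from the change. In a GEE check the interaction was 0.781 with and without the main effect, and 0.729 once status x visit was added. In 200 simulated two-visit trials with 20% dropout, the mean standard error stayed at 0.254 with the main effect added. The gains in step 3 therefore need a status x visit term or a change/ANCOVA model.

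**The case against.** The strongest reply is that this is an optional precision covariate in a study that calls itself a pilot. Randomisation already protects the comparison, the unadjusted standard error already allows for chance imbalance, and the average gain for mood is small. All of that stands, and it limits the point to an improvement.

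Several stronger readings are tempting, and the documents do not support them.
- A reader might infer that the treatment comparison is biased. It is not: an imbalance in entry status would arise by chance.
- A reader might infer that the sample is a mixture. Table 1 permits one, but no proportions are given, and the requirements for current MA, MDD, HAMD and CGI-S narrow it.
- A reader might take MA status as the main driver of outcome in every aim. No section ranks drivers. The background ties stopping MA to low mood and reports lower PCr in users, but it does not say that entry urine predicts the eight-week course of either. Dysphoria described as persistent may even argue against steeply different courses.
- A reader might think that a woman who enters MA-negative cannot gain MA-free tests. The outcome is a count over eight weeks, not a change from entry, so prevented relapse raises her count.

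A positive/negative result also cannot separate women who have just stopped from those long abstinent, so part of the withdrawal effect would stay unadjusted.

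**Conclusion.** The point holds as a worthwhile, nearly free improvement. Entry is open on recency of use, the urine result is scheduled before treatment, and neither the randomisation nor any stated model uses it. Under the assumed ranges the average gain for mood is modest: 75 women act like 76-87. Imbalances above 20 points, which would matter for reading a single result, have a 6-8% chance at 75 women and 2-3% at 123. For the MA-free-test count the gain runs from negligible (76) to large (150), depending wholly on assumed shares, and that outcome is exploratory. Baseline HAMD or the other covariates may already carry part of this information, which would shrink the mood gain. No size is given for PCr, NAA or cognition, because the documents offer nothing to base one on.

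**What to change.** - Define baseline MA status as the last MA urine result before randomisation (positive/negative). Screening may run over two or three visits, so the choice of result needs stating.
- MA-free-test comparison: name a model and include baseline MA status as a covariate.
- Aims 1-3: enter baseline MA status x visit (with its main effect), or use status as a covariate in a change/ANCOVA model. A main effect alone is not enough where baseline is a response visit.
- If the randomisation list can still be changed, stratify by this status. If not, prespecified adjustment remains available.
- Do not adjust for MA use after randomisation. The plan treats it as an outcome that creatine may change, and its remark that GEE allows time-varying covariates should not be read as licence to do so.

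Cost: no new data, and one or two degrees of freedom per model where visit has two levels or is linear. If weekly HAMD visits are modelled as categories, the interaction takes one for each visit after baseline. Settling this before unblinding also avoids a choice driven by whatever imbalance turns up.

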The proposed study will use a randomized, double-blind, placebo-controlled design. 123 participants will be randomly assigned in a 1:1 ratio to placebo or 5 grams of daily creatine treatment for eight weeks. We also plan to recruit 24 age-matched females (18-55).

STUDY PROCEDURES

All procedures performed by study personnel are research-related. None of the study activities will be considered standard of care. There will be no cost to study subjects for their participation. Participants will be compensated for their time and travel. Table 2A and 2B outlines the schedule of study procedures for treated participants and healthy controls.

Consent will be obtained before any study procedures are initiated. Potential participants will be informed of the study and offered a consent form to review. They will be encouraged to discuss study participation with their relatives. If a potential participant expresses interest in study participation, the informed consent process will be conducted. After the informed consent process, individuals will be offered time to consider study participation and to ask questions. Subjects and parents/guardians will have the opportunity to discuss the study with a study team member in a setting free of coercion. The language of the informed consent form is written at a level easily understood by the subject and any questions asked by the subject will be answered honestly and free of bias. A specific meeting time will be set up between a study team member and the participant where the entire informed consent document will be carefully explained in its entirety. The length of the meeting will be designed so there is the necessary amount of time for all questions to be answered.

Randomization of participants to the two treatment conditions will take place according to a randomization list generated prior to the start of recruitment. 47 (50%) will be randomized to placebo. The study will be conducted as a double-blind trial, with neither participants nor research staff aware of participant assignment. Except in cases of medical emergency, the double-blind will not be "broken" until recruitment is closed and the final participant has completed 8 weeks of treatment with investigational drug. There is no "washout period" for any participant in this study, and participants randomized to placebo will continue treatment with a psychotropic medication throughout their time in the study.

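### Baseline antidepressant use is recorded at screening but is not a planned covariate, which gives up a little precision in the HAMD and BAI comparisons and leaves them open to a shift if the arms are unbalanced

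*Combined protocol and SAP*

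**What the plan says.** **Who is admitted.** Table 1 makes background medication conditional: "If taking a psychotropic medication for depressed mood, regimen must be stable for ≥ 4 weeks prior to randomization". A woman taking nothing for mood can therefore also enter. Study Procedures rules out a washout and adds that "participants randomized to placebo will continue treatment with a psychotropic medication throughout their time in the study".

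**What is recorded.** Table 2A lists "Concomitant Medications" and "Treatment Program Attendance" at screening and in every week from 1 to 11.

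**How women are allocated.** Participant Selection Criteria states that "123 women will be randomly assigned in a 1:1 ratio to either creatine or placebo for eight weeks". Study Procedures says only: "Randomization of participants to the two treatment conditions will take place according to a randomization list generated prior to the start of recruitment". No stratification factor, blocking or minimisation is described.

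**How outcomes are modelled.** The Overall Analytic Strategy uses GEE for metabolites, depression and anxiety symptoms, and cognitive tests, with one covariate set for all: "We will control for age, other drug abuse, anxiety scores, and tissue partial volume effects in each GEE model". Neither background antidepressant use nor programme attendance is in it. The section does not say how baseline HAMD or BAI enters the model.

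**The concern.** On the Table 1 wording the sample can mix medicated and unmedicated depression. Background medication is a plausible predictor of how HAMD and BAI move over eight weeks, and its value before randomisation is already collected. The covariate list nonetheless puts tissue partial volume, an imaging quantity, into every model while leaving this variable out of the mood models.

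Two things are at stake. First, any outcome variance that background medication explains stays in the error term. Second, in a trial of this size the arms can differ noticeably in the share medicated, and an unadjusted estimate then carries part of that difference. Programme attendance raises the same question. The evidence for it is weaker, because the Resources section describes what the recruiting clinic offers, including "free groups for individuals awaiting Salt Lake County funded substance abuse treatment services", and not the programme status of the women enrolled.

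**Working it through.** **The plan's own figure.** Overall Power and Sample Size Calculations sets the mean of eight on-treatment HAMD scores against the mean of two baseline scores, with average effect 0.25 (read here as SD units), correlation 0.5 and 75 women. It reports an effective effect size of 1.09 and power 0.87.

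- With equal correlation 0.5, Var(y\*) = (1 − 0.5) × (1/8 + 1/2) = 0.3125, so SD(y\*) = 0.559.
- Effective effect size = 0.25 / 0.559 = 0.447, not 1.09.
- Two-sample power with 37.5 per arm and two-sided alpha 0.05 (assumed, as none is stated for HAMD) is 0.48 by noncentral t and 0.49 by the normal approximation.

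The stated figures were not reproduced. That is a separate matter and this point does not depend on it. The variance of 0.3125 is used below as the working value.

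**Assumptions.** The documents give neither of these: *p*, the share medicated at baseline, taken as 0.2 to 0.5; and *b*, the difference medication makes to the average on-treatment course, taken as 0.2 to 0.5 SD.

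**Size of chance imbalance.** Under simple 1:1 randomisation, the SD of the arm difference in share medicated is √(4p(1 − p)/N).

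| N | p | SD of gap | 95% limit | P(gap ≥ 10 points) |
|---|---|---|---|---|
| 75 | 0.2 | 0.092 | ±0.181 | 0.28 |
| 75 | 0.5 | 0.115 | ±0.226 | 0.39 |
| 123 | 0.2 | 0.072 | ±0.141 | 0.17 |
| 123 | 0.5 | 0.090 | ±0.177 | 0.27 |

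Both totals are shown because the protocol randomises 123 in one place and powers on 75 in another.

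**Shift given an imbalance.** Shift = gap × b. At N = 75 and the 95% limit:

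- smallest: 0.181 × 0.2 = 0.036 SD;
- largest: 0.226 × 0.5 = 0.113 SD.

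The range is about 0.04-0.11 SD, against a planned average of 0.25. The standard error of the arm difference is 0.559 × √(2/37.5) = 0.129, so even the largest shift is below one standard error (0.113 / 0.129 = 0.88).

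**Power with and without the covariate** (N = 75, p = 0.5, normal approximation). Unadjusted variance is 0.3125 + b² × 0.25; adjusted variance is 0.3125.

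| b | Unadjusted variance | Power unadjusted | Power adjusted |
|---|---|---|---|
| 0.2 | 0.3225 | 0.48 | 0.49 |
| 0.3 | 0.3350 | 0.46 | 0.49 |
| 0.5 | 0.3750 | 0.42 | 0.49 |

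With p = 0.2, where p(1 − p) = 0.16, the gain at b = 0.5 is smaller: unadjusted variance 0.3525 and power 0.45, against 0.49 adjusted.

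The GEE section assumes a first-order autoregressive structure. If the correlation of 0.5 is instead the lag-one value over ten equally spaced scores, SD(y\*) is 0.936 and the variance 0.876. At p = 0.5 and b = 0.5 medication then inflates the variance by 0.0625 / 0.876 = 7% instead of 20%, and the power gain is about 0.01 (0.20 to 0.21).

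**Simulation of the contrast without the covariate** (N = 75, p = 0.5, b = 0.3 and 0.5; 6,000 runs per scenario).

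- Type I error was 0.048-0.052.
- Among runs with a gap of 15 points or more in one direction, the shift was about 0 when medication moved only the stable level, which is also present at baseline. It was 0.06-0.10 SD when medication altered the on-treatment course.

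**The case against.** A sponsor can fairly answer that nothing here is broken. Randomisation makes the comparison unbiased on average, and the standard error already allows for chance imbalance. A regimen that has been stable for four weeks before randomisation mostly affects a woman's level, and that cancels when treatment scores are set against baseline scores. All of this stands. One qualification is that the GEE text does not say how baseline enters. If the model compares treatment visits without it, level differences would enter too.

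The size also rests on assumed inputs, and the power gain is small over most of the range. No gain has been computed for programme attendance. Both criticisms stand and are why the point is minor.

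Read literally, the Study Procedures sentence about placebo participants continuing a psychotropic suggests that all of them take one, whereas the Table 1 wording is conditional. The two passages must be reconciled. The point assumes a mix of medicated and unmedicated women; if every woman were medicated, the covariate would be constant and would gain nothing.

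A reader might infer three stronger things that the documents do not support:

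- *That background treatment biases the HAMD and BAI result.* It does not on average, and type I error is preserved.
- *That the list is known to be unstratified.* The protocol is silent on how it was built; all one can say is that no stratification is described.
- *That the trial fails by not showing whether creatine works alone or only on top of an antidepressant.* Aim 2 asks only whether creatine is superior to placebo on HAMD and BAI.

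**Conclusion.** The point holds as a minor matter of precision and of protection against chance imbalance. Antidepressant use at screening is collected, plausibly prognostic, and absent from both the covariate list and the description of randomisation. At N = 75, with 20-50% medicated and a 0.2-0.5 SD effect on the on-treatment course (both assumed), an imbalance at the 95% limit moves the estimate by about 0.04-0.11 SD against a planned 0.25. Adjustment adds about 0.01-0.07 to power. The upper ends need the largest assumed effect, half the women medicated, and equal correlation of 0.5 between visits. The validity of the treatment test is not in question.

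**What to change.** In the Overall Analytic Strategy, prespecify antidepressant use at the screening visit (yes/no) as a baseline covariate in the HAMD and BAI GEE models. Programme attendance at screening (yes/no) may be added as an option.

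The form depends on the model, so the text should first say how baseline HAMD and BAI enter:

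- If the model compares arms over the treatment visits, enter the covariate as a main effect.
- If baseline is one of the responses and the effect is a treatment-by-visit term, add a covariate-by-visit term. A main effect alone does little for that contrast.

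Use screening values only. Medication and attendance are also recorded weekly, and the section notes that GEE permits time-varying covariates, but values after randomisation may themselves be affected by treatment and should not be adjusted for.

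The cost is one or two degrees of freedom, slightly more with visit terms, and no new data collection. The wording sits in the combined protocol, so under Reporting Protocol Changes it needs IRB and FDA approval and the agreement of the NIDA program officer before use. Changing the randomisation list is not proposed: it needs the same approvals, and the covariate recovers the precision at issue.
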